6.2.2 Analysis of Secondary Outcomes of Interest

The number of identified HIV-positive male partners per woman will be compared between study groups using the same GEE approach as described above; an offset accounting for differing numbers of partners will be included if possible. For each woman, the second outcome (proportion of unprotected sexual encounters with individuals who were HIV-positive or whose HIV status was unknown) will be defined as a binary variable that indicates whether the proportion is below a threshold of 0.10 – this will distinguish between women who engaged in a high degree of safe sexual behavior and those who did not. This outcome will be analyzed similarly to the first, but the GEE model of interest will assume a logit link and binomial distribution.

Aim 2 data analysis will consist of 5 steps: 1) Reading for Content: Our analysis will begin with data reading until content becomes intimately familiar [45]. As data are reviewed, emergent themes will be noted. Topics that the research has not adequately addressed and ones that emerge unexpectedly will be explored in continued fieldwork. 2) Coding: A list of codes will be created based on identified themes and assigned to specific sections of text so that the text can be easily searched. Code definitions will be documented in a code book [46]. Qualitative interviewers will be trained to apply the codes using ATLAS.ti. To ensure inter-coder reliability, 10% of data will be double-coded. 3) Data reduction: Once transcripts have been coded, we will work within each code to identify principal sub-themes that reflect finer distinctions in the data. This entails taking an inventory of what is related to the given code, capturing the variation or richness of each theme and noting differences between individuals or among subgroup [46]. 4) Data display: Matrices and tables that categorize and display data will be used to help facilitate comparisons. 5) Interpretation: Once text has been read and coded, and central ideas extracted, we will identify and explain the core meanings of the data. We will search for relationships among themes identified and develop diagrams in order to map out relationships in the data.

Aim 3. Our analyses will estimate the cost per averted disability-adjusted life year (DALY) based on (a) increased identification of HIV-positive men, and thus higher and earlier initiation of ART; and (b) fewer HIV infections among women as a result of using self-tests to make safer sexual decisions. Our analyses will include modeled lifetime ART health benefits and costs. Our analyses will also be useful for estimating how many additional high-risk men can be tested and how many additional HIV infections can be averted by spending a fixed amount of resources on self-tests rather than conventional testing models. Analyses will be conducted using customized spreadsheet-based decision tree and clinical progression simulation modeling methods adapted from other projects. Extensive one-way, multi-way, threshold, and scenario sensitivity analyses will quantify the effects of input uncertainty on results. Our analytic perspective will be the health system, for direct medical costs, discounting future costs and DALYs at 3% per year.

CONFIDENTIAL

7 Safety and Adverse Events

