3.3 Study Measures

An original questionnaire was developed for to assess various participant characteristics at baseline. This questionnaire includes questions about participant's socio-economic characteristics, sexual behavior, HIV testing history as well as the PHQ-9 mental health scale and a gender-based violence assessment. Follow-up data will be obtained through short surveys as well as a follow-up questionnaire administered at approximately 6-month intervals.

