3.4.2 Secondary Study Endpoints

Number of male partners per participant who obtain an HIV-positive test result. This information will be obtained directly from the index participants. For each participant, we will assess the number of reported partners who tested for HIV and obtained a reactive result. We hypothesize that the number of HIV-positive male partners identified per participant will be higher in the intervention group than the comparison group.

Proportion of unprotected sexual encounters with partners who were HIV-positive or whose HIV status was unknown. This outcome will be based on data from follow-up surveys and will assess the HIV risk that participants were exposed to during the follow-up period. We expect, based on pilot data, that women in the intervention group will be able to utilize self-tests to facilitate HIV results disclosure with sexual partners and make safer sexual decisions. Thus, we hypothesize that the intervention group will be less likely than the comparison group to have unprotected sex with a partner of unknown or HIV-infected status.

Additional Outcomes. Other outcomes that we assess will include the occurrence of intimate partner violence (IPV), discussion of HIV testing with partners, and occurrence of couples testing. The outcomes of Aim 2 will be a qualitative narrative of how HIVST are perceived and used. Aim 3 will use the primary outcome to determine the cost-effectiveness of HIVST distribution in this setting.

4 Study Population and Duration of Participation

The study will include women who report having two or more partners in the past month, including women who exchange sex and high-risk women residing in beach communities. In each of the selected clusters (hotspots or beach communities), we will sample women and assess their eligibility. We will also interview male partners of women who participate in the study, to collect data on their experience. Women enrolled in the main study will be followed for up to two years. Male partners who are contacted will participate in one qualitative interview.

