Participants in the clusters randomized to the control group will be provided with several HTS referral vouchers initially and encouraged to distribute them to their sexual partners (participants will be informed they can return for additional vouchers during the follow-up period of up to 24-months. As in the intervention group, participants in the comparison group will also be counseled on the importance of condom use and other sexual risk reduction strategies. Female participants will also be encouraged to give their male partners a phone number that they can contact if they have questions.

For both study arms, research assistants will seek to recruit those who meet eligibility criteria. Research assistants will review the written informed consent form with eligible women and those who provide written consent to study enrollment will be administered a baseline questionnaire (described below), and digital fingerprint collection with a fingerprint biometric device to verify identification at follow-up visits. We have found fingerprinting to be highly acceptable, and it has been successful in other studies in the region.

Data Collection Procedures:

Baseline data. At the time of enrollment, participants will be administered a baseline questionnaire to record information such as socio-demographic characteristics, economic characteristics, sexual behavior, HIV testing history, and any experience of IPV.

Distribution Visits. Participants will be offered the opportunity to collect additional HIVST or VCT referral coupons regularly during the follow-up period. These visits will entail the distribution of the study tools, retraining on important counseling messages (how to safely avoid IPV, importance of condom use, etc.) and collect basic information on how the study tools previously distributed were used. IPV and other possible adverse events will be monitored at every point of contact.

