6.2 Statistical Methods

6.2.1 Analysis of Primary Outcome of Interest

The annual incidence of HIV infection will be compared between study arms through regression modeling using a generalized estimating equations (GEE) approach with a log link and assumed Poisson response distribution (the negative binomial distribution will be used if this distribution is not valid). An offset will be used in this model to account for differential follow-up times. The model will contain a dichotomous covariate for study group; the two-sided ($\alpha = 0.05$) statistical significance of the associated regression coefficient will be assessed with a Wald test performed using robust standard errors. If there are differences in baseline characteristics between the two study groups, a second regression model will be constructed that adjusts for the differing baseline characteristics.

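### The sexual-risk secondary outcome has no fixed denominator, and its baseline adjustment depends on an undefined imbalance between the arms

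*Combined protocol and SAP*

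**What the plan says.** Section 3.4.2 names the endpoint as "Proportion of unprotected sexual encounters with partners who were HIV-positive or whose HIV status was unknown". It says that the data come from follow-up surveys, and it hypothesises that "the intervention group will be less likely than the comparison group to have unprotected sex with a partner of unknown or HIV-infected status". It gives no denominator and no cut-point.

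Section 6.2.2 turns the endpoint into a yes/no variable per woman, "defined as a binary variable that indicates whether the proportion is below a threshold of 0.10", and gives the purpose: "this will distinguish between women who engaged in a high degree of safe sexual behavior and those who did not". It then says "This outcome will be analyzed similarly to the first", with a logit link and binomial distribution. The first secondary outcome in turn uses the GEE approach of section 6.2.1. There the main model holds study group only and, if baseline characteristics differ between the groups, "a second regression model will be constructed that adjusts for the differing baseline characteristics". No criterion for a difference is given and no covariate is named.

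Baseline sexual behaviour is collected. Section 3.3 lists "socio-economic characteristics, sexual behavior, HIV testing history as well as the PHQ-9 mental health scale" among the baseline questionnaire topics, and section 5 (Data Collection Procedures) says that "participants will be administered a baseline questionnaire to record information such as socio-demographic characteristics, economic characteristics, sexual behavior" will be recorded.

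**The concern.** The endpoint's name supports two readings: risky unprotected encounters as a share of all encounters, or as a share of unprotected encounters only. The second is the literal one. It has no value for a woman who always used condoms, and it can score more condom use as less safe, against the purpose stated in section 6.2.2. This is one of two main secondary outcomes and the only one of them on sexual behaviour. The trial is unblinded (section 3.2), so the definition should be settled before any comparison by arm.

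Two further gaps affect the same number. Follow-up lasts 12 to 24 months (section 5), so women will have different numbers of 6-monthly surveys, and section 15.1 also lists monthly text-message surveys. Nothing says which surveys count or how they are combined. Nor is there a rule for a woman who reports no encounters.

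Separately, whether to adjust, and for what, is decided only after baseline data have been compared by arm. A measure likely to predict this outcome is already collected, but the plan does not commit to using it.

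**Working it through.** **The plan's own figure.** Only HIV incidence is powered. The unmatched cluster formula for rates, with 0.045 and 0.0225 per year, a coefficient of variation of 0.40 and 30 × 1.5 × 0.90 = 40.5 woman-years per cluster (section 6.1), gives

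1 + 7.849 × [(0.045 + 0.0225)/40.5 + 0.16 × (0.045² + 0.0225²)] / 0.0225² = 33.12 clusters per arm.

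That rounds to 33 per arm, or 1,980 women. The figure reproduces and does not depend on this outcome. The plan gives no expected level, spread or effect for the sexual-risk outcome.

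**Exact examples.** Let n = encounters, u = unprotected encounters, and r = unprotected encounters with a partner of positive or unknown status. The candidates are r/n and r/u.

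| Woman | r/n | r/u |
|---|---|---|
| n = 20, u = 4, r = 1 | 0.05, below | 0.25, not below |
| n = 20, u = 12, r = 1 | 0.05, below | 0.083, below |
| The same woman, condoms at 4 more encounters with known-negative partners: u = 8 | 0.05, below | 0.125, not below |
| n = 20, u = 0, r = 0 | 0, below | 0/0, undefined |

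Because u ≤ n, r/n never exceeds r/u. Every disagreement is therefore a woman who is below 0.10 on all encounters and not below on unprotected encounters only.

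**How often the class differs (assumed inputs).** Simulation of 400,000 women per setting. Encounter counts are negative binomial (size 2, minimum 1) with mean 20 or 60. The share unprotected and the share risky among unprotected each vary between women as a beta distribution with a + b = 2 or 5. With both shares averaging 30%:

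- Among women with any unprotected encounter, about 61-67% are below 0.10 on all encounters and 25-45% on unprotected only.
- The class differs for 18-39% of these women.
- About 4-23% of all women are 0/0 on the unprotected-only reading.
- With each mean share at 10%, 30% or 50%, the class differs for 7-56% of women with any unprotected encounter.

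**Baseline covariate (assumed inputs).** Simulated trials had 33 clusters per arm, 27 women per cluster (30 less 10%), a cluster SD of 0.3 on the logit scale, and a GEE with robust cluster standard errors. Efficiency is the squared ratio of mean Wald z, adjusted (standardised risk difference) over unadjusted, for the below-0.10 outcome. The observed correlation between baseline and follow-up was 0.10-0.61.

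| Cluster differences persisting from baseline | Efficiency factor |
|---|---|
| None | 0.98-1.11 |
| Half | 1.05-1.28 |
| Full | 1.08-1.59 |

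In one half-persistence setting, power rose from 0.493 to 0.593. These powers correspond to mean z of about 1.94 and 2.20, and (2.20/1.94)² ≈ 1.28.

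**False-positive rate.** Suppose that adjustment is triggered by a 5% test on the baseline item and that significance in either model counts. The simulated null rejection rate was then 4-7%. All the trial simulations ignore the matching of clusters on population and type (section 3.2).

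**The case against.** The case for leaving the text alone has real content. The hypothesis in 3.4.2 and the purpose in 6.2.2 both favour all encounters, and the perverse condom example arises only on the other reading. The questionnaires are attachments that are not shown. The adjustment rule keeps an unadjusted model and reaches this outcome only through two cross-references. All of this stands and limits the size of the point. It does not supply a denominator, a 0/0 rule or a covariate, and a questionnaire would not replace an analysis definition.

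A reader might infer more than the documents support:

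- *That cutting at 0.10 wastes power.* Not in general. In simulations the efficiency of the cut relative to the proportion ran from 0.63 (uniform odds ratio of 0.75, mean proportion 0.4) to 5.1 (8% of intervention women moving to zero risk). The hypothesis, worded as being less likely to have such sex, partly suits a binary form.
- *That conditional adjustment inflates false positives.* The simulated rates were 4-7%.
- *That the covariate would be omitted from most trials.* That assumes a significance test as the trigger, and the plan states no trigger.

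**Conclusion.** The point holds as a gap in specification of a main secondary outcome. The exact examples need no assumption: the two readings can give opposite classes, and one of them leaves consistent condom users without a value. How many women are affected is not known from the documents. The 18-39% and 4-23% figures rest on assumed shares of 30% and an assumed spread between women.

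The adjustment part is smaller. What is lost is a plan fixed in advance and a possible gain in efficiency. The factor of 0.98-1.59 runs from no gain to a useful one, depending on the assumed correlation and the persistence of cluster differences, and it comes from unmatched simulations. The analysis of HIV incidence and its sample size are not touched.

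**What to change.** 1. In section 6.2.2, define the proportion as unprotected encounters with partners of positive or unknown status divided by all reported encounters, so that women who always use condoms score 0. State which follow-up surveys count, how they are combined over 12 to 24 months, and how women with no encounters are handled, with a sensitivity analysis of that last rule. Settle this before data are compared by arm.
2. In the GEE for this outcome, include one named baseline sexual-behaviour item and the matching factor cluster type (hotspot or beach), whatever imbalance is seen. Report the unadjusted model alongside, and a standardised (marginal) contrast, because the adjusted odds ratio is conditional on the covariates.
3. Optional: state a basis for 0.10 and add an analysis on the proportion scale. Neither scale is better in general, so this is a matter of preference.

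The cost is SAP wording, one more model to report and a rule for missing baseline values. It needs no new data, provided the questionnaires hold the items.

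### Aim 3 does not carry the sampling error of the trial's own clustered estimates jointly into the cost per DALY averted

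*Combined protocol and SAP*

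**What the plan says.** Section 6.2.2 holds the whole analysis plan for Aim 3. The result measure is set out as follows: "Our analyses will estimate the cost per averted disability-adjusted life year (DALY) based on" two pathways. The first is "increased identification of HIV-positive men, and thus higher and earlier initiation of ART"; the second is "fewer HIV infections among women as a result of using self-tests to make safer sexual decisions". The tools are "customized spreadsheet-based decision tree and clinical progression simulation modeling methods adapted from other projects". On uncertainty there is one sentence: "Extensive one-way, multi-way, threshold, and scenario sensitivity analyses will quantify the effects of input uncertainty on results". The perspective and discounting are given as "Our analytic perspective will be the health system, for direct medical costs, discounting future costs and DALYs at 3% per year".

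Section 3.4.2 links the model to the trial: "Aim 3 will use the primary outcome to determine the cost-effectiveness of HIVST distribution in this setting". The primary outcome is HIV incidence. The number of HIV-positive male partners identified, which is the natural trial source for the first pathway, is a secondary endpoint reported by the same women.

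Sections 6.2.1 and 6.2.2 plan GEE models for both endpoints, with robust standard errors. No section mentions a probabilistic sensitivity analysis, a bootstrap, a confidence or credible interval, or an acceptability curve for Aim 3.

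**The concern.** Both trial inputs to the model are estimates from about 66 clusters. Each carries sampling error. Because they come from the same women in the same clusters, their errors may be correlated, although the documents give neither the sign nor the size of that correlation.

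Varying inputs over chosen ranges shows how sensitive the answer is to each of them. It does not give the probability that the intervention is cost-effective, or an interval that reflects how precisely the trial measured its effect. The plan makes clustered inference for the endpoints and then does not say how it passes into the economic result.

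At stake is how firm the cost per DALY will look to those deciding on scale-up, which is a stated purpose of Aim 3. The gap matters most if the observed effect is modest. The difference in infections may then be compatible with no benefit, where a cost-per-benefit ratio has no finite upper limit. The plan words both pathways as gains and does not say what will be reported in that case.

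**Working it through.** **Inputs (section 6.1; two-sided test from section 6.2.1).** Control incidence 0.045 per year; 50% reduction, so 0.0225; 33 clusters per arm; 30 women per cluster; 1.5 years of follow-up; 10% loss; between-cluster coefficient of variation k = 0.40; alpha 0.05; power 80%.

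**Step 1: reproduce the plan's sample size.** Person-years per cluster: y = 30 × 1.5 × 0.9 = 40.5. The usual unmatched formula for comparing rates in a cluster trial is

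c = 1 + (1.96 + 0.84)² × [(r0 + r1)/y + k²(r0² + r1²)] / (r0 − r1)²

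- (r0 + r1)/y = 0.0675/40.5 = 0.001667
- k²(r0² + r1²) = 0.16 × (0.002025 + 0.000506) = 0.000405
- Sum = 0.002072; (r0 − r1)² = 0.000506
- c = 1 + 32.12 = 33.12 per arm (32.12 without the added 1)

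This agrees with the stated 33 per arm and 1,980 women. Power at 33 per arm is about 80% with the added 1 and 81% without it. The sample size is not in dispute; the point is that this variance model matches the plan's design.

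**Step 2: sampling error of infections averted at the design values.** Each arm has 33 × 40.5 = 1,336.5 person-years, with about 60 and 30 infections expected.

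- SE of the rate difference = √(0.002072/33) = 0.0079
- 95% interval: 0.0225 ± 1.96 × 0.0079 = 0.0070 to 0.0380
- Infections averted: 2.25 per 100 woman-years, 0.70 to 3.80

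**Step 3: effect on cost per infection averted, incremental cost held fixed (unrounded limits used).**

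- Best case: 2.25/3.803 = 0.59 times the point value
- Worst case: 2.25/0.697 = 3.2 times the point value
- Span: 3.803/0.697 = 5.5-fold

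**Step 4: smaller observed effects (assumed rate ratios, same variance formula).**

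| Observed rate ratio | Averted per 100 woman-years | 95% interval |
|---|---|---|
| 0.5 | 2.25 | 0.70 to 3.80 |
| 0.6 | 1.80 | 0.19 to 3.41 |
| 0.7 | 1.35 | −0.31 to 3.01 |
| 0.8 | 0.90 | −0.82 to 2.62 |

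At 0.7 and 0.8 the interval includes zero, so the ratio has no finite upper limit.

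**Step 5: check on another scale.** Section 6.2.1 plans a log-link model. At the design values the SE of the log rate ratio is 0.244, so the 95% interval is 0.31 to 0.81. With the control rate fixed at 4.5 per 100, infections averted run from 4.5 × (1 − 0.807) = 0.87 to 4.5 × (1 − 0.310) = 3.1, about 3.6-fold. This leaves out error in the control rate, so it is the narrower account.

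**What cannot be computed.** The documents give no unit costs, DALY weights or progression inputs, so no interval for cost per DALY can be derived from them.

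**The case against.** The strongest reply is that section 6.2.2 promises extensive work on input uncertainty, and the trial's effect is an input. The GEE model supplies confidence limits that could set the ranges. Analyses varying several inputs at once move them together, and a threshold analysis can show the effect size at which the conclusion changes. The plan never says that correlation will be ignored. This stands in part: nothing forbids using the trial's limits. But nothing plans it either, and separate limits run through these techniques would not produce a joint interval or a probability.

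A second reply is that the 5.5-fold span is not about the headline measure. That is correct. A reader might take it as the uncertainty in cost per DALY, and the documents do not support that reading. The span covers the incidence pathway only and holds incremental cost fixed, whereas averted infections also change modelled lifetime ART costs. It depends on the scale (Step 5) and sets aside the matching in section 3.2.

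A reader might also infer that Aim 3 counts no harm, because both pathways are worded as benefits. That goes too far. Extra infections from false-negative results or riskier sex would enter through the net incidence difference if it is used as estimated. Intimate partner violence is indeed absent from the DALY account. It is, however, measured as an outcome (section 3.4.2), followed up case by case, and covered by the DSMB's review of risk and benefit (section 7.4.3). Section 10.1 reports one adverse event with 370 self-tests distributed in the pilot. The documents give no disability weight for violence, so converting it to DALYs is a debatable modelling choice, and its absence is not an error in the plan.

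**Conclusion.** The point holds as an omission. Followed as written, Aim 3 yields a cost per DALY averted with no joint statement of the trial's own sampling error.

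That error is not small on the incidence pathway. Even if the planned halving is observed exactly, the interval for infections averted is 0.70 to 3.80 per 100 woman-years. Weaker effects, at a rate ratio of 0.7 or above, are compatible with no benefit. These figures assume unmatched variance and a coefficient of variation of 0.40 in both arms. The 5.5-fold span also assumes fixed incremental cost. Effective matching would probably narrow the intervals; by how much cannot be told from the documents.

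Aim 3 is a secondary aim (section 2.2). The primary test and its error rate are not affected, so this is a worthwhile improvement that does not threaten the trial's main conclusion.

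**What to change.** Add a probabilistic analysis to the Aim 3 text in section 6.2.2:

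- Resample clusters in a way that respects the matched randomisation of section 3.2 (matched pairs or strata).
- In each draw, recompute the incidence difference and the number of HIV-positive men identified together, so that any correlation is carried through.
- Use the net incidence difference as estimated, and keep draws that show no benefit.
- Draw the remaining inputs from distributions stated in advance.
- Report incremental cost and incremental DALYs with intervals, net monetary benefit and an acceptability curve. Give an interval for the cost-per-DALY ratio only when the interval for the DALY difference excludes zero.
- Keep the deterministic analyses already listed as supportive.

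Optionally, show the by-arm difference in intimate partner violence beside the cost-effectiveness result, without converting it to DALYs.

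The trial inputs need no new data collection. The cost is some extra analyst time, including choosing and documenting distributions for the other inputs, and a wider stated range around the headline figure.
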